of doing mental health research with high-risk participants. Relationships with referral agencies include Apache Behavioral Health Services, Rainbow Treatment Center and Indian Health Services Social Services Department. Research staff will encourage both adult and youth participants to disclose their use to parents with research staff support in order to engage a familial support system for youth related to opioids. Our staff will remind the participant of the study protocol which would have been explained to them during consent. A participant may refuse the opioid abuse assessment at the time of the study visit. In this case, they would be required to have the opioid abuse assessment conducted before the next intervention or study visit to continue in the parent grant and supplement.

Note: Parent/guardian will be notified during the consent process that their child's responses to the items on the study instruments will not be shared with them. However, if immediate triage of study participants is required due to the identified worsening of symptoms or using or abusing opioids, the Research Program staff member will notify the parent/guardians of the <18 year old participants at the same time that the appropriate tribal authorities are notified. For study participants aged 18-19, it is not required that the Research Program staff notify the parent or guardian, but Research Program staff will attempt to do so with the study participant's verbal permission.

Aim 3: We expect minimal risk, however, [name], a clinical psychologist, and be available if unexpected issues arise.

2. If a Data Safety Monitoring Board (DSMB), or equivalent will be established, describe the following:

This section only applies to Aim 1. Aim 3 will not have a DSMB.

- a. The DSMB membership, affiliation and expertise.

The Data and Safety Monitoring Board (DSMB) will be comprised of a group of independent experts that advises the Southwest Hub and will include at a minimum, one suicide expert, one tribal nations expert, and one biostatistician.

- b. The charge or charter to the DSMB.

The DSMB will meet at least once yearly via phone conference calls for the duration of the project. They will assist the study in monitoring adverse events. At the initial meeting the DSMB will review and approve all study protocols before study initiation to ensure participant safety. Protocols will include formal procedures for reporting and tracking all adverse reactions to the NIH and IRBs; tracking progress in the study; and identifying any need for premature termination of the protocol. At subsequent meetings, the DSMB will be provided with summary study progress reports and adverse events. The DSMB will provide a summary report following each meeting. The DSMB will conduct interim analyses of data prior to end of study to closely monitor effectiveness and any possibility of harms associated with the programs.

- c. Plans for providing DSMB reports to the IRB.

Annual reports will be prepared by the Clinical Research Supervisor and report any risks identified, what steps were taken to mitigate them and any new areas of risk that need attention.

All types of adverse events will be summarized for the DSMB and reviewed during their meetings. The DSMB will also review participant safety and confidentiality, and data safety. Specifically, the DSMB will be asked to evaluate:

- 1) all serious, unexpected and commonly experienced adverse events, including those related to opioids, or other unanticipated problems that involve risk to study participants, regardless of whether these events appear related to the study-based interventions or research assessment protocols;
- 2) whether participants' safety, privacy, and confidentiality has been consistently assured by the investigators;
- 3) whether data is being managed, stored, and maintained in accordance with scientific standards; and
- 4) the risk/benefit ratio to determine if it has changed to the extent that the study should be modified or discontinued.

4. Describe plans for interim analysis and stopping rules, if any.

Stopping rules will be established by the DSMB prior to study initiation.

In cases where participants score in the high-risk category on the Opioid Risk Tool, the local research staff will consult with the two Co-PIs to determine if the participant can continue in the parent study. The parent study is an effectiveness trial, where participants can receive other services as necessary. The main factor for deciding whether they can continue in the trial is whether participating in our study is interfering with them participating in needed opioid treatment (i.e., participation in our trial may be a barrier to the time commitment needed for substance use treatment) or vice versa—i.e., participation substance abuse treatment may be a barrier to the time commitment needed to participate in our trial.

D. Reporting Unanticipated Problems/Adverse Events (AE's) to the IRB (all studies must complete this section):

Aim 1 & 3: Describe your plan for reporting to the IRB and (if applicable) to the sponsor. Include your plan for government-mandated reporting of abuse or illegal activity.

The Research Program staff will immediately alert the Local Project Director and PIs in the event of an adverse event or unanticipated problem. The PIs, Drs. [name] and [name], and the Clinical Research Supervisor, [name], will report serious adverse events to the JHSPH IRB if it is unanticipated, poses risk of harm to participants or others, and is related to the study. If there is any suspected harm to self, others, or abuse reported during an interview (including those related to opioid use), the Research Program staff will immediately report this information to the PIs. The PIs and the Local Project Director will report this to appropriate Tribal or Law Enforcement Authorities. With experience from previous studies with the White Mountain Apache community, the study team is knowledgeable of how to report this type of event without revealing study participation.

NOTE: The IRB does not require submission for all AEs, only those that are **unanticipated, pose risk of harm to participants or others, and are related to the study.**

E. Other IRBs/Ethics Review Boards:

If other IRBs will review the research, provide the name and contact information for each IRB/ethics review board and its Federal Wide Assurance, if it has one (available on OHRP's website at <http://www.hhs.gov/ohrp/assurances>).

This project was approved by the White Mountain Apache Tribal Health Board and the White Mountain Apache Tribal Council. (Note: White Mountain Apache Tribal Health Board and Tribal Council approval was granted simultaneously when the grant application was submitted to conduct the research).

F. Collaborations with non-JHSPH Institutions:

For studies that involve collaboration with non-JHSPH institutions, complete the chart below by describing the collaboration and the roles and responsibilities of each partner, including the JHSPH investigator. This information helps us determine what IRB oversight is required for each party. Complete the chart for all multi-collaborator studies.

Insert Name of Institutions in Partner column(s); add additional columns if necessary.

| | JHSPH | Partner 1 | Partner 2 |
|-------------------------|-------|-----------|-----------|
| Primary Grant Recipient | X | | |
| Collaborator | | | |

For the following, indicate “P” for “Primary”, “S” for “Secondary” (as appropriate to role and level of responsibility.) Add additional items if useful.

| | | | | |
|----|-----------------------------------------------------------------------------------------------------------------------------------------------------------------------|---|--|--|
| 1. | Human subjects research ethics training for data collectors | P | | |
| 2. | Day to day management and supervision of data collection | P | | |
| 3. | Reporting unanticipated problems to the JHSPH IRB/Sponsor | P | | |
| 4. | Hiring/supervising people obtaining informed consent and/or collecting data | P | | |
| 5. | Execution of plan for data security/protection of participant data confidentiality, as described in the Data Security and Confidentiality Protections section above . | P | | |
| 6. | Biospecimen processing, storage, management, access, and/or making decisions about future use | P | | |

XI. Secondary Data Analysis of Existing Data:

A. Study Design:

1. Describe your study design and methods. The study design must relate to your stated aims/objectives.

The study design and method is the same as for the Southwest Hub aim 1, see section III.A.

2. Provide an estimated sample size and an explanation for that number.

The study sample size is the same sample population described in aim 1, see section III.B.

3. Provide a brief data analysis plan and a description of variables to be derived.

See section V.4.

B. Participants:

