Aim 1: We will randomize **304 participants**; 76 to CM alone, 76 to CM+NH, 76 to CM+ ER, and 76 to CM+NH+ER. Based on the previous work with the SIQ, we believe a 25% reduction among individuals with a score of 30 or greater would represent clinically significant change in suicide ideation.[5] Using pilot data of NH among the WMAT, an average baseline score of 45 could be expected on the SIQ.[5] A clinically significant reduction translates into a large Cohen's D effect size (>0.8). However, we want the power to observe the more moderate effect expected to result from comparing the sequencing of the interventions (NH+ER vs. NH+CM vs. CM+ER vs. CM alone). Using an adjusted alpha to account for multiple comparisons of 0.013, and a correlation of 0.2 among repeated measures, with four groups (NH+ER vs. NH+CM vs. CM+ER vs. CM alone), $n=58$ people per group ($n=116$ randomized at each randomization time-point) would provide 80% power to detect a small to moderate effect (Cohen's $F=0.2$). Adjusting these estimates for 30% attrition would result in $n=76$ per each of the four groups ($n=152$ per arm) for a total sample size of $N=304$.

Please note for our ***the Opioid Data Collection Sub-Study***: We will use a mixed methods approach to examine opioid use among our SMART trial participants through addition of a quantitative opioid related measure and qualitative interviews ($N=30$) with a subset of those who endorse recent or current use.

For the economic evaluation supplement: We will use the same sample of participants as Aim 1. We are not drawing statistical inferences about cost estimates so there is no sample size requirement. Instead, we are reporting on the health care services utilization and costs incurred by study participants before, during and after the intervention. To administer a time use survey and conduct in-person interviews we will use all HUB program case managers (five or more) and healthcare providers (three or more).

For the diversity supplement: We will use a sub-sample of $n=239$ WMAT participants enrolled in the parent trial. This sample size is based on the estimated enrollment rates during the Diversity Supplement study period.

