After 30 days from CM3, all youth will be visited by Research Program Assistants and complete a fourth assessment (CM4). The 30-day time frame between CM3 and CM4 will allow ample time to complete the ER intervention with participants and assess any changes in resilience across study groups. To track long-term outcomes, all youth will complete a final assessment 3 month later (CM5: 6 months post-enrollment). All youth will be followed to the end of the study period (up to 4.75 years from the first participant’s enrollment) for any subsequent suicide events using the Apache surveillance system. If necessary, assessments may be conducted over the phone for participants who start in the study but are located elsewhere during an assessment timepoint.

As part of the economic evaluation supplement, our staff will be asked to fill out time logs listing how they spent time the preceding day. This will not affect the study participants in any way.

Aim 3: STUDY PROCEDURE

If stakeholders provide informed consent, they will be interviewed by Drs. [name] or [name] using a semi-structured guide to gather their views on the Southwest Hub’s key intervention components (Surveillance/Case Management, New Hope and Elders’ Resilience Interventions). They will also be asked to participate in a 2x annually administered online survey to better understand how capacity for sustainability changes over time. If they consent to the online survey, the Program Sustainability Assessment Tool (PSAT) will be administered via email to participants every six months.

2. Describe the number and type of study visits and/or contacts between the study team and the participant, how long they will last, and where/how they will take place.

Aim 1: Five study visits will take place over the course of 6 months. All study visits will take place in the participants' home or a private location.

CM1: Recruitment, consent, randomization, baseline assessment: 2 hours

Intervention Group: NH: 2-4 hours

CM2: Assessment: 1 hour

CM3: Assessment and randomization: 1 hour

Intervention Group: EC: 2-4 hours

CM4: Assessment: 1 hour

CM5: Assessment: 1 hour

Opioid Data Collection Sub-Study (for a subset): Additional 60-90 minutes interview

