Aim 3: The qualitative interview should take no longer than 45 minutes and will be done at a convenient time. There will only be one-two study visits, although stakeholders will be encouraged to provide feedback at any time about their experiences with the Southwest Hub's key intervention components. For the online survey, the survey is expected to take 20 minutes and will be administered twice a year in years 2-5, for a total of 8 time points. *The opioid roundtables are estimated to take 60-90 minutes.*

4. Provide a brief data analysis plan and a description of variables to be derived.

Primary and Secondary Outcomes

Aim 1: Given the longitudinal nature of the data, we will use mixed-effects regression models (MRMs)[41] to estimate average treatment effects while accounting for shared variance of repeated measures within adolescent. MRMs are highly flexible, addressing: variability in number and spacing of measurements, a variety of outcome distributions, linear and non-linear patterns of change (e.g., quadratic), and are robust to missing data.

Suicide ideation (primary outcome): Measured by the Suicide Ideation Questionnaire (SIQ/SIQ-JR). The SIQ is a 15-item scale that analyzes frequency and severity of suicidal ideation over the past 6 months. Items are scored on a 7-point scale ranging from 0 “I never had this thought” to 6 “Almost every day.” Scores of 30 for the SIQ and 23 for the SIQ-JR indicate severe suicidal ideation and need for clinical intervention. The scale has been used among AI adolescents with sound psychometric properties (Cronbach’s alpha=0.97).[22]

Resilience (secondary outcome): Measured by The Resiliency Scales. These are self-report scales measuring the individual’s Sense of Mastery (MAS; composed of 20 items), the Sense of Relatedness (REL; 24 items), and the Emotional Reactivity (REA; 20 items). Each item has five response choices ranging from 0 (Never) to 4 (Almost Always).

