| Voices of Indian Teens Cultural Issues and Interest | X | X | X | X | X | | |
| Rosenberg Self Esteem Scale | X | X | X | X | X | | |
| Index of local indicators of well-being | X | X | X | X | X | | |
| COVID-19 Questions | X | X | X | X | X | | |
| Exit Interview Questions | | | | | X | | |
| Opioid Data Collection Sub-Study: Opioid Follow-Up Interview (offered at first assessment point they endorse use) | X | X | X | X | X | | |
| JHU Acceptability | | | | | | | X |
| JHU Feasibility | | | | | | | X |
| Program Sustainability Assessment Tool (PSAT) | | | | | | | X |
| Opioid Roundtables (when stakeholders are available) | X | X | X | X | X | | |
| Implementation Qualitative Interview | | | | | | | X |
| Session Summary Form | | X | X | X | X | | |
| Additional Case Management Form | | | As needed | | | | |
| Work Absenteeism | X | X | X | X | X | | |
| PROMIS Pediatric Anxiety Short Form | X | X | X | X | X | | |

Qualitative: In-depth interviews will use semi-structured theoretically driven interview guides and will be transcribed and thematically coded using emergent coding. From the quantitative data, item frequencies and summary scale scores will be examined to identify barriers and facilitators to program acceptability, feasibility and sustainability.

For the opioid guide, we consulted with other researchers examining substance use in Native American populations to create our semi-structured guide (see Appendix).

5. **Answer the following if they are relevant to your study design:**

A. If the study has different arms, explain the process for assigning participants (intervention/control, case/control), including the sequence and timing of the assignment.

Aim 1: Participants will be stratified by age groups (10-14, 15-19, 20-24, 25-29) and event type (ideation, attempt, binge + recent ideation), then randomized to the control or intervention condition using a 1:1 assignment ratio. Re-randomization of all participants will occur again at CM3 (another 30 days or 60 days/2 months post-baseline assessment).

Aim 3: N/A

B. If human biospecimens (blood, urine, saliva, etc.) will be collected, provide details about who will collect the specimen, the volume (ml) and frequency of collection, how the specimen will be used, stored, identified, and disposed of when the study is over. If specimens will be collected for use in future research (beyond this study), complete the “Biospecimen Repository” section below.

N/A

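### The 30% attrition allowance was computed as 58 × 1.3 instead of 58 / 0.7, so 304 participants keep the required 58 per sequence only up to about 24% attrition

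*Combined protocol and SAP*

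**What the plan says.** Section III.B, Aim 1, plans 76 participants in each of four sequences. The calculation starts from an adjusted alpha of 0.013, "a correlation of 0.2 among repeated measures, with four groups", and Cohen's f of 0.2. It concludes that "n=58$ people per group ($n=116$ randomized at each randomization time-point) would provide 80% power". The attrition step follows directly: "Adjusting these estimates for 30% attrition would result in $n=76$ per each of the four groups", which is 152 per arm and 304 in total. The inflation formula is not printed, and neither the test nor the number of repeated measures is given.

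Three other places bear on the point. Section V.C.5.A places the second randomisation at the third visit ("Re-randomization of all participants will occur again at CM3"), so the four sequences exist only from then on. Section V.C.1 schedules two assessments after it, CM4 at 90 days and CM5 at 180 days. Section V.C.4 names mixed-effects regression as the Aim 1 analysis and says that it accommodates "variability in number and spacing of measurements". No other section gives a different attrition rate or adjustment.

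**The concern.** Attrition is a share of those randomised. If 30% are lost, the required number must be divided by 0.70. Multiplying it by 1.30 adds 30% of the smaller number and leaves too few. The paragraph reads as a promise that 58 per sequence, and with them the stated 80% power, remain after a 30% loss. On the plan's own figures they do not.

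This is the only sample-size justification for the primary aim. Anyone monitoring follow-up against it would take 58 per sequence as still secured at, say, 28% loss, when it is not. Losses are foreseeable: section V.C.5.F removes participants who move off the reservation or are relocated for treatment, and section X.C allows discontinuation linked to opioid use.

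**Working it through.** **Inputs, all from section III.B, Aim 1:** 58 required per sequence; attrition 30%; 76 per sequence and N = 304 after adjustment; four groups; alpha 0.013; correlation 0.2; f = 0.2; power 80%.

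**1. Reproduce the plan's figure.** n × (1 + d) = 58 × 1.30 = 75.4, rounded up to 76; 76 × 4 = 304. This matches exactly.

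**2. Number needed to retain 58.** n / (1 − d) = 58 / 0.70 = 82.86, rounded up to 83; 83 × 4 = 332. Shortfall: 332 − 304 = 28. Division by 0.70 cannot give 76.

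**3. What 304 delivers at 30% attrition.** 76 × 0.70 = 53.2 per sequence; 304 × 0.70 = 212.8, about 213 in total. The requirement is 58 × 4 = 232, so the shortfall is about 8%.

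**4. Attrition that 304 does absorb.** 1 − 58/76 = 0.237, or 23.7%.

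Steps 1 to 4 need no assumption beyond the plan's own numbers.

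**5. Power, conditional on an assumed test.** The plan does not state the test or the number of measures m. I assumed the between-subject F test of a repeated-measures analysis with k = 4 groups: λ = N f² m / (1 + (m − 1)ρ), with 3 and N − 4 degrees of freedom, f = 0.2 and ρ = 0.2. I ran it at the stated alpha of 0.013 and at 0.0125 (0.05/4, which rounds to 0.013).

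| m | Minimum n per group for 80% power (alpha 0.0125 / 0.013) | Power at n = 53 (alpha 0.0125 / 0.013) |
|---|---|---|
| 1 | 95 / 94 | 46.4% / 46.9% |
| 2 | 58 / 57 | 76.0% / 76.4% |
| 3 | 45 / 45 | 88.2% / 88.4% |
| 4 | 39 / 39 | 93.4% / 93.6% |
| 5 | 35 / 35 | 96.0% / 96.1% |

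Only m = 2 gives about 58. It also equals the number of assessments after the second randomisation, although the plan does not say that this was the basis. With m = 2, power at 58 per group is 80.9% (alpha 0.0125) or 81.3% (alpha 0.013). A group-by-time F test with the same f and ρ, using λ = N f² m / (1 − ρ), does not reproduce 58: its minimum n is 39, 32, 27 and 24 for m = 2 to 5, and power at 53 is at least 93%.

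**6. Possible offset from partial data (m = 2, assumption).** A completer contributes information 2/1.2 = 1.67 and a dropout with one of the two visits contributes 1. At 30% attrition there are 22.8 dropouts per group.

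| Share of dropouts with one visit | Power (alpha 0.0125 / 0.013) |
|---|---|
| 0% | 76.2% / 76.6% |
| 25% | 79.7% / 80.1% |
| 50% | 82.7% / 83.1% |
| 100% | 87.7% / 88.0% |

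The first row uses 53.2 per group, hence the small difference from 76.0% / 76.4% at 53.

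**The case against.** The arithmetic is hard to dispute; the case on the other side is that it matters little.

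- **Headcount is not power.** Under the two-measure reading at alpha 0.013, 57 per group already gives 80%, and 25% attrition leaves exactly 57 (76 × 0.75). The power shortfall is therefore confined to roughly 25–30% attrition and is at most about 4 points below 80%. This stands, and it limits the practical size of the error.
- **Dropouts may still contribute.** The planned mixed model uses incomplete records, and if a quarter of dropouts supply one of the two later visits, power at 30% attrition is back to about 80%. This stands as a possibility. However, the sample-size paragraph takes no such credit: it makes an explicit headcount adjustment. Under the two-measure reading, anyone lost before the second randomisation has no later data to contribute.
- **The power figure is a reconstruction.** The test and the number of measures are inferred from the fact that they return 58. This also stands, so 76% should be read as conditional. It does not touch the headcount result.
- **No decision rule is tied to attrition.** The plan sets no stopping or enrolment rule based on 58 per group or on 30% loss. That is correct. The consequence is a misleading statement of what the design tolerates, not a wrong trial action.

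**Conclusion.** The error is real. The adjustment multiplies by 1.3 where it should divide by 0.7. The planned 304 is 28 short of the 332 that the stated rule requires, leaves about 53 per sequence at 30% attrition, and protects 58 per sequence only up to 23.7%. These figures follow from the plan alone.

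The cost in power is moderate and less certain: about 76% against about 81% at 30% attrition, if the calculation was a four-group test on two measures and dropouts contribute nothing. Other numbers of measures give 46% to 96% at 53 per group, but none of them reproduces 58. Usable data from dropouts would shrink or remove the loss. The point should be corrected, but it does not undermine the design.

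**What to change.** Keep 304 and replace the last sentence of the Aim 1 sample-size paragraph in section III.B with:

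> With 76 per group (N = 304), at least 58 per group complete if attrition is at most about 24%; at 30% attrition about 53 per group (213 in total) complete.

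In the same edit, name the test and the number of repeated measures behind 58, and give the power at 53 per group on that basis (about 76% if it was a four-group test on two measures). If credit is taken for partial follow-up in the mixed model, state the assumed share of dropouts with usable data after the second randomisation.

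The cost is wording only, with no extra participants: the stated tolerance falls from 30% to about 24%, or the stated power at 30% attrition becomes slightly lower. Keeping the 30% claim as written would instead mean 83 per sequence, 332 in total.
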